1.0 Background & Rationale

Endoscopic resection of large benign lesions is the preferred treatment over surgical resection.

Endoscopic mucosal resection (EMR) is associated with a lower risk and cost compared to surgical treatment. However, it is important that patients undergo endoscopic follow-up after piecemeal EMR in approximately 6 months because there is an approximately 25% risk of recurrence of adenoma polyps ¹.

A randomized controlled trial in only 24 patients showed a significant reduction of the recurrence rate by treatment of the normal appearing perimeter of the EMR defect using the argon plasma coagulator ². A recent non-randomized trial suggested a substantial reduction by treatment of the perimeter with the snare tip in the soft coagulation mode ³.

In this study we are proposing a randomized controlled trial to test Argon Plasma Coagulation (APC) versus Snare Tip Soft Coagulation (STSC) vs no treatment. In a previous trial of APC, the recurrence rate of the control arm was very high at 67%. With only 24 patients in the study the actual benefits of APC remain uncertain. The previous study using STSC was a non-randomized trial. In this trial we hope to provide definitive evidence regarding the efficacy of APC and STSC vs control.

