2.0 Objective(s)

2.1 Primary Objective

To investigate the efficacy of APC or STSC in reducing the recurrence rate at the first follow-up after polypectomy of large colon polyps

Hypothesis:

APC or STSC treatment of the perimeter of the EMR defect will reduce the recurrence rate of adenomas when compared to our control of no treatment.

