9.0 Data Safety Monitoring

See Data and Safety Monitoring Board Charter for information about DSMB. Briefly, the data safety monitoring board comprises 4 members: [name] MD (Indiana University), [name] PhD (Indiana University), [name] MD (Henry Ford Hospital), and [name] MD (Chair), (Medical University of South Carolina). None of the board members are involved with the current study in any capacity. Additionally, [name] research team will provide him up to date information regarding the status of patients and any reportable events.

The data collected at sites other than IU will be de-identified before being sent to us. Each site will enter their data in to a secure web application (REDCap), which will then be accessed at the primary site. Only de-identified data from external sites will be added to the database (no HIPAA identifiers will be collected from external sites besides procedure dates and de-identified images of study lesions). Any other communication that is not patient related will be done over email or phone.

Variables that will be transmitted from the other site include:

- Information from the procedure to remove the large polyp
 - This includes information about meeting inclusion/exclusion criteria, procedure date, randomization envelope number/randomization treatment, age, gender, race,

ethnicity, whether a fellow was involved in the procedure (and which parts of procedure, if applicable), procedure times, study polyp characteristics, de-identified study lesion images, resection times, information about the resection such as snare/ injection fluid usage and number of resected pieces, treatment times, other additional treatments used, clipping times, number/type of clips used, type of colonoscope used, Boston Bowel Preparation Score, whether fibrosis was present, whether there were any prior attempts at resection, information about procedural complications (if any), and study polyp pathology results

- Information from the 30 day follow up call
 - This includes information about whether the follow-up phone call was made successfully, date subject was reached by phone, and whether patient reported experiencing adverse events (and if so, information about the adverse event).
 - Information from the first follow-up procedure

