11.0 Statistical Considerations

Assuming a 25% recurrence rate of the control arm, and a reduction to 10% in both of the treatment arms, we estimate that a sample size of 115 subjects per arm will be needed to demonstrate that APC and STSC are superior to no treatment for reduction of recurrence rate after EMR, based on 80% power and a two-sided 5% significance level for comparison of independent proportions with one interim analysis. The no treatment arm will be used as our control. In order to account for drop-outs, an extra 35 patients will be enrolled into the study to ensure sufficient data will be included in the analysis. Therefore, a sample size of 380 subjects will be enrolled in this study.

Once a polyp has been identified and its size fits within the targeted range, each subject will be randomized in a 1:1:1 ratio using a computer generated randomization sequence. Enrollment into the study will be competitive with the possibility for each site outside of IU to randomize up to 100 patients. Not all 645 randomization numbers generated will be used in the study. Instead each external site will continue to enroll until a total of 380 patients have been randomized study-wide with a potential to randomize up to 100 patients. Randomization numbers will be assigned as follows: IU will be assigned numbers 001 – 095 and 496 - 526; AdventHealth Orlando will be assigned 096 – 145 and 446 - 470; The Johns Hopkins Hospital will be assigned numbers 146 – 195; Dartmouth-Hitchcock Medical Center will be assigned numbers 196 – 245; NYU Langone Medical Center will assigned numbers 246 – 295 and 471 - 495; the Mount Sinai

Hospital will be assigned 296 – 345, Sibley Memorial Hospital will be assigned 346 – 395, the University of Kansas Medical Center will be assigned 396 – 445, and Penn State Health Milton S. Hershey Medical Center will be assigned 546 - 595. The proportion of subjects with recurrence will be compared between study arms using chi-square tests. The number of complications will be compared among treatment arms using negative binomial regression. Treatment times and costs will be compared between the APC and STSC arms using Wilcoxon Rank Sum tests. A 5% significance level will be used for all tests.

Interim analysis and stopping rule:

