The interim analysis will be conducted after half of the subjects have completed the study, using an O'Brien-Fleming spending function with alpha levels 0.003 and 0.049 at the interim and final analyses. Any results will be considered significant at a p-value of ≤ 0.003 at the interim analysis and the DSMB will make a decision about stopping the study based on those results.

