12.0 Statistical Data Management

Primary data will be collected via case report forms. All paper charts pertaining to the patient will be kept under lock and key in coordinators office away from the endoscopy area. Each site will enter their data in to a secure web application (REDCap). Virtual data will be stored on an internal network drive with encryption and password security. Only approved personnel by the IRB will have access to the file storage. This file will also not have any identifiable patient information. A study log with the identifiable information will be kept in a separate folder to enable the investigators to assist in any research audit. No procedural data except the date of examination will be entered into this log.

The storage location on IU servers will be backed up automatically and continuously. Quality assurance steps will include built in range checks for age, procedure duration, lesion size, total resection time, treatment time, clipping time on REDCap and remote study site visits after completion of the study by 190 patients.

Remote study site visit:

Before interim analysis and after completion of the study by 190 patients, 10% of case report forms from each site will be verified with the site's electronic medical system information via a video based call from the central data site (IU). Any patterns of systematic errors will trigger the verification of all case report forms for that particular site.

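### Does the interim rule need changing because it does not say what follows if only one treatment crosses 0.003?

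*Combined protocol and SAP*

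**What the plan says.** Section 11.0 plans one interim analysis when half the subjects have completed, with O'Brien-Fleming spending and "alpha levels 0.003 and 0.049 at the interim and final analyses". The rule itself is short: "Any results will be considered significant at a p-value of ≤ 0.003 at the interim analysis", after which "the DSMB will make a decision about stopping the study based on those results". Section 12.0 places a data check "Before interim analysis and after completion of the study by 190 patients", which puts the look at about half of the 380 enrolled.

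The aim is worded in two ways. The hypothesis in Section 2.1 is that "APC or STSC treatment of the perimeter of the EMR defect will reduce the recurrence rate of adenomas" compared with no treatment. Section 1.0 says "In this trial we hope to provide definitive evidence regarding the efficacy of APC and STSC vs control", and Section 11.0 sizes the trial "to demonstrate that APC and STSC are superior to no treatment for reduction of recurrence rate after EMR".

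Section 3.1 makes adenoma recurrence at the first follow-up colonoscopy the only primary outcome. Section 11.0 names the untreated arm as control and gives chi-square tests for recurrence. On the board, Section 9.0 says "See Data and Safety Monitoring Board Charter for information about DSMB"; the charter is not among the documents.

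**The concern.** With two treatments sharing one control, an interim look can end with one comparison past the boundary and the other short of it. The rule covers results of any kind with a single threshold and does not mention this case. Read literally, it does not even confine itself to recurrence against control.

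The wording of the aim seems to make this worse. If success means either treatment, one crossing answers the question. If it means both, one crossing leaves half the question open, and the chance of answering it depends on how the second comparison is then tested. A handling chosen after the interim results are known would be data-dependent. If the board stopped the study on one crossing and the second comparison were dropped, much of the power to show both treatments superior would go with it.

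**Working it through.** **Inputs.** From Section 11.0: recurrence 25% (control), 10% (APC), 10% (STSC); 115 per arm; 1:1:1 allocation; levels 0.003 and 0.049, i.e. |z| ≥ 2.968 and 1.969. Interim size per arm: 115/2 = 57.5, taken as 57, or 190/3 = 63.3, taken as 63. The plan does not say whether the chi-square test is continuity-corrected, so both forms are shown.

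**The plan's own figures.**
- Uncorrected n per arm = [1.960·√(2·0.175·0.825) + 0.842·√(0.25·0.75 + 0.10·0.90)]² / 0.15² = 100 at 5%, and 101 at 4.9%.
- With continuity correction, n′ = (n/4)·[1 + √(1 + 4/(0.15n))]² = 113 and 114. This agrees with 115 to within 2.
- 3 × 115 + 35 = 380.
- O'Brien-Fleming-type spending at half information gives 0.00305 at the interim and 0.0490 at the end. Levels of 0.003 and 0.049 together use 0.04998 for one comparison.

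The stated numbers therefore hold.

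**How often the open case arises.** Simulation with 2,000,000 trials per setting and a shared control; z = (p_c − p_t)/√(2p̄(1 − p̄)/n), with 1/n taken off the absolute difference for the corrected test.

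| At the interim | 57 per arm, plain (corrected) | 63 per arm, plain (corrected) |
|---|---|---|
| At least one crosses | 0.276 (0.192) | 0.334 (0.233) |
| Both cross | 0.074 (0.045) | 0.100 (0.055) |
| Exactly one crosses | 0.202 (0.147) | 0.234 (0.178) |

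One-only crossings are 0.202/0.276 = 73% and 0.234/0.334 = 70% of all crossings (76–77% corrected).

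**What the handling costs.** Chance that both treatments are shown superior:

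| Handling after a one-arm crossing | 57 per arm, plain (corrected) | 63 per arm, plain (corrected) |
|---|---|---|
| Other comparison runs to 115 per arm | 0.782 (0.714) | 0.782 (0.714) |
| Accrual stops; other tested at 0.049 on 100 per arm | 0.775 (0.709) | 0.773 (0.708) |
| Same, 90 per arm | 0.769 (0.706) | 0.767 (0.704) |
| Same, 75 per arm | 0.760 (0.698) | 0.755 (0.692) |
| Study stops; other never tested again | 0.593 (0.578) | 0.566 (0.552) |

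The 75–100 per arm already randomized is an assumption, because the plan gives no accrual rate. The loss from stopping accrual runs from 0.782 − 0.775 = 0.007 to 0.782 − 0.755 = 0.027 (corrected: 0.714 − 0.709 = 0.005 to 0.714 − 0.692 = 0.022). With no retest it is 0.782 − 0.593 = 0.189 to 0.782 − 0.566 = 0.216 (corrected: 0.136 to 0.162). The chance of showing at least one treatment superior is about 0.95 (0.92) under every handling.

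**Error rates.** If only APC works (25/10/25, an assumption), testing STSC again at 0.049 gives it a false-positive rate of 5.0% at 115 per arm and 5.0–5.1% at 75–100 per arm. If neither works, the rate is about 5.0% per comparison and 9.0% for at least one of the two (6.4% corrected).

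**Which handling the text supports.** The interim rule follows directly on the sizing paragraph, which concerns recurrence on APC and STSC against no treatment with one interim look. Section 3.1 lists no other primary outcome. The final level of 0.049 is not withdrawn for a comparison that misses at the interim. Sections 5.0 and 7.0 schedule a follow-up colonoscopy for all randomized patients as standard of care, so their outcomes would still arrive after accrual stopped. The handling that fits these passages is to test the other comparison at the end on everyone randomized, which is one of the rows with a small loss.

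On the aim, Section 2.2 speaks of timing each treatment and joins APC and STSC with the same conjunction as Section 2.1. There it plainly means each of the two, since both are timed and then compared. Read that way, Section 2.1 agrees with Sections 1.0 and 11.0.

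**The case for a change.** The best case for a change is that the gap is real, not rare, and cheap to close. On the plan's own assumptions the unaddressed outcome has a 15–23% chance and makes up most efficacy crossings. Confirmatory testing of the second arm belongs in the analysis plan whatever the charter says, and writing it down beforehand removes any suspicion that it was chosen to suit the results. If either treatment alone counts as success, two comparisons at these levels carry about 9% family-wise error, which the plan does not mention.

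Much of this stands as description: the text is silent on a one-arm crossing, and a sentence in Section 11.0 would be a courtesy to the reader. It does not show that the plan as written leads to a wrong analysis. The large loss depends on two steps the plan does not take: an automatic stop on one crossing, and abandonment of the other comparison. The decision rests with a board independent of the study, which is a legitimate design choice, and its charter may already cover the case. On multiplicity, statisticians differ on whether two treatments each compared with a shared control need adjustment; stating a view would inform readers but correct no error.

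**Conclusion.** No change is called for. The interim rule is brief and leaves a one-arm crossing open, but the surrounding text identifies the two comparisons, keeps a final test at 0.049 and schedules outcomes for every randomized patient. Filled in that way, stopping accrual early on one crossing costs about 0.5 to 2.7 points of the chance to show both treatments superior, and the second comparison's false-positive rate stays at about 5%. The differing conjunctions in Sections 1.0, 2.1 and 11.0 are most likely everyday usage.

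This rests on the plan's rates of 25/10/10, an interim at 57 or 63 per arm, an assumed 75–100 per arm randomized when accrual stops, and no drop-out beyond those numbers. It would need another look if the unseen charter required the whole study to end, without further testing, as soon as one treatment crossed; then the loss would be 14–22 points.

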12.0 Statistical Data Management

Primary data will be collected via case report forms. All paper charts pertaining to the patient will be kept under lock and key in coordinators office away from the endoscopy area. Each site will enter their data in to a secure web application (REDCap). Virtual data will be stored on an internal network drive with encryption and password security. Only approved personnel by the IRB will have access to the file storage. This file will also not have any identifiable patient information. A study log with the identifiable information will be kept in a separate folder to enable the investigators to assist in any research audit. No procedural data except the date of examination will be entered into this log.

The storage location on IU servers will be backed up automatically and continuously. Quality assurance steps will include built in range checks for age, procedure duration, lesion size, total resection time, treatment time, clipping time on REDCap and remote study site visits after completion of the study by 190 patients.

Remote study site visit:

Before interim analysis and after completion of the study by 190 patients, 10% of case report forms from each site will be verified with the site's electronic medical system information via a video based call from the central data site (IU). Any patterns of systematic errors will trigger the verification of all case report forms for that particular site.

